#### Evaluation of overall response

Target lesions	Non-Target lesions	New Lesions	Overall response
CR	CR	No	CR
CR	Non-CR/Non-PD	No	PR
CR	NE	No	PR
PR	Non-PD or NE	No	PR
SD	Non-PD or NE	No	SD
NE	Non-PD or NE	No	NE
PD	Any	Yes or No	PD
Any	PD	Yes or No	PD
Any	Any	Yes	PD

CR = complete response, PR = partial response, SD = stable disease, PD = progressive disease, NE = not evaluable

#### Special notes on response evaluation

*Missing assessments and non-evaluable designation:* When no imaging/measurement is done at all at a particular time point, the patient is not evaluable (NE) at that time point. If only a subset of lesion measurements are made at an assessment, usually the case is also considered NE at that time point, unless a convincing argument can be made that the contribution of the individual missing lesion(s) would not change the assigned time point response. This would be most likely to happen in the case of PD.

*Symptomatic progression:* Patients with a global deterioration of health status requiring discontinuation of treatment without objective evidence of PD at that time should be reported as “symptomatic deterioration.” Every effort should be made to document objective progression even after discontinuation of treatment. Symptomatic deterioration is not a descriptor of an objective response: it is a reason for stopping study treatment.

*Confirmation of response:* Confirmation of response (by repeat scans after 4 weeks or as specified in the protocol) is required for studies in which response rate is the primary endpoint, but is not required in randomized studies or studies with primary survival endpoints (i.e., where response is not a primary endpoint).

CONFIDENTIAL

Study Drug: AC176

Sponsor/Development Innovations Study Number: AC176-001/GU 207

Final Protocol: 10 July 2023 Version 4.0

## ASSESSMENT OF BONE LESION PROGRESSION USING PCWG3 CRITERIA

The same method of assessment and the same technique should be used to characterize each identified and recorded lesion at baseline and during follow-up visits.

### Baseline imaging

The use of  $^{99m}\text{Tc}$ -methylene diphosphonate radionuclide bone scintigraphy should be used, with the presence or absence of metastasis recorded. A quantitative measure of disease burden, such as lesion number, the bone scan index, or lesion area, is recommended. Changes in lesions considered metastatic on bone scintigraphy should be followed, assessed, and recorded. Areas/lesions on bone scans that are suggestive can be assessed further with CT or MRI and followed separately, but this supplemental imaging should not be used to establish lesions for the purposes of the trial.

### Bone scan progression

For progression, pseudoprogression should be excluded in the absence of symptoms or other signs of progression. The 2+2 rule (at least two new lesions on the first post-treatment scan, with at least 2 additional lesions on the next scan) should be used to distinguish flare from true progression. If at least 2 additional new lesions are seen on the next (confirmatory) scan, the date of progression is the date of the first post-treatment scan (i.e. when the first 2 new lesions were documented).

For scans after the first post-treatment scan, at least 2 new lesions relative to the first post-treatment scan should be confirmed on a subsequent scan. The date of progression will be the date of the scan that first documents the second lesion. Changes in intensity of uptake alone do not constitute either progression or regression. The proportion of patients who have not progressed at fixed time points (6 or 12 months) should be reported.

### Bone lesions

- Bone scan, PET scan or plain films are not considered adequate imaging techniques to measure bone lesions. However, these techniques can be used to confirm the presence or disappearance of bone lesions.
- Lytic bone lesions or mixed lytic-blastic lesions, with identifiable soft tissue components, can be considered measurable if the soft tissue component meets the definition of measurability described above.
- Blastic bone lesions are considered non-measurable.

*CONFIDENTIAL*

Study Drug: AC176

Sponsor/Development Innovations Study Number: AC176-001/GU 207

Final Protocol: 10 July 2023 Version 4.0

## OVERALL RADIOLOGICAL VISIT ASSESSMENT

Table 7 provides the definitions how the visit responses for soft tissue (according to RECIST1.1 criteria) and bone progression status (according to PCWG3 criteria) are combined to give an overall radiological objective visit response.

**Table 7      Overall radiological response – RECIST v1.1 and bone progression (PCWG3)**

Overall visit soft tissue response (RECIST 1.1)	Bone progression status (PCWG3)	Overall radiological response
CR	No bone lesions at baseline	CR
CR, target lesions were present at baseline	Non-PD or NE	PR
CR, only non-target lesions present at baseline	Non-PD or NE	Non-CR/Non PD
PR	Non-PD or NE	PR
SD	Non-PD or NE	SD
No soft tissue lesions at baseline	Non-PD or NE	Non-PD
PD	Any	PD
Any	PD	PD

CR = complete response, PR = partial response, SD = stable disease, PD = progressive disease, NE = not evaluable

## **Appendix C: Prostate Cancer Working Group 3 (PCWG) PSA Criteria**

### Baseline/Study Entry

PSA progression requirements for study entry

Patients must have measurable PSA  $\geq 1.0$  ng/mL as the minimum starting level for trial entry if the confirmed rise is the only indication of progression (excluding pure small cell carcinoma). It is recommended to estimate a pretreatment PSA doubling time (PSADT) if at least 3 values are available  $\geq 4$  weeks apart. Treatment or enrollment onto a trial should not be delayed to estimate PSADT.

### On-Study Disease Assessments

- PSA results are to be collected on Day 1 of each treatment cycle
  - Continue through early rises for a minimum of 12 weeks unless there is other evidence of progression, as favorable effects on PSA may be delayed for  $\geq 12$  weeks
  - Ignore PSA rises before 12 weeks in determining PSA response

Patients with PSA progression are allowed and encouraged to continue treatment until symptomatic or radiographic progression.

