- o Bone scans - technetium only -  $\leq$ 4 weeks prior to initiation of treatment, every 2 cycles (8 weeks)  $\pm$ 5 days up to 24 weeks, then every 12 weeks  $\pm$ 5 days, and at the End of Study visit if scans were not taken in the previous 8 weeks. Bone lesions should be evaluated using PCWG3 criteria and not RECIST v1.1.
- p An EOT visit should be performed for all patients who permanently discontinue study treatment. If the decision to permanently discontinue treatment is made at a scheduled visit, the EOT visit should be performed instead of the scheduled visit (preferably within 7 days and no later than 14 days after the last treatment).
- q All patients will be followed during the off-treatment period until all treatment-related toxicity resolves, or for at least 30 days post-study drug discontinuation, or until the start of another anti-cancer treatment. Any concomitant medications received up to 30 days after the last dose of study medication should be recorded.
- r Follow-up for PD visits for tumor assessment by imaging (CT scan/MRI/bone scan, if applicable) for patients who discontinue study treatment without having PD based on RECIST v1.1 (see [Appendix B](#)) should be performed as on treatment until PD or another withdrawal criterion is met (see Section [7.5.3](#)). At these visits, serious adverse events (SAEs) occurring during the study that are considered to be related to study treatment or procedures will be followed until resolution.

*CONFIDENTIAL*

Study Drug: AC176

Final Protocol: 10 July 2023 Version 4.0

Sponsor/Development Innovations Study Number: AC176-001/GU 207

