### **3.3 Discontinuation from Study Treatment**

Patients will be discontinued from study treatment for any of the following reasons:

- Disease progression (Patients who are receiving clinical benefit in the opinion of the treating Investigator may be allowed to stay on study after consultation with the Medical Monitor)
- Irreversible or intolerable toxicity or clinically significant abnormal laboratory values thought to be related to drug toxicity
- Conditions requiring therapeutic intervention not permitted by the protocol
- Intercurrent illness (this will be at the Investigator's discretion)
- Inability of the patient to comply with study requirements
- Patient lost to follow-up
- Patient requests to discontinue treatment
- Patient withdraws consent from study treatment or study participation altogether
- Study termination.

After discontinuation from protocol treatment, patients must be followed for adverse events (AEs) for 30 days after their last dose of study drug. All new AEs occurring during this period must be reported and followed until resolution unless, in the opinion of the Investigator, these

*CONFIDENTIAL*

Study Drug: AC176

Sponsor/Development Innovations Study Number: AC176-001/GU 207

Final Protocol: 10 July 2023 Version 4.0

AEs are not likely to improve because of the underlying disease. In this case, the Investigator must record his or her reasoning for this decision in the patient's medical records and indicate that the outcome is not resolved on the AE pages on the electronic case report form (eCRF).

All patients who have Grade 3 or 4 laboratory abnormalities (per CTCAE Version 5.0) at the time of treatment discontinuation must be followed until the laboratory values have returned to Grade 1 or 2 unless, in the opinion of the Investigator, it is not likely that these values are to improve. In this case, the Investigator must record his or her reasoning for making this decision in the patient's medical records and indicate that the outcome is not resolved on the AE pages on the eCRF.

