## **5.2 Treatment Duration**

The **start of the study** is defined as the date when the first patient in the whole study signs informed consent.

The **end of the study** is defined as the date of the last visit (including all follow-up visits) of the last patient in the whole study.

Patients will be evaluated for toxicity at the start of each cycle. Restaging will occur with CT/MRI or bone imaging as defined in the applicable SOA (see [Table 2](#) or [Appendix H](#)). Patients will continue on treatment until disease progression as defined in [Appendix B](#) and [Appendix C](#) or intolerance of side effects.

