#### **7.4.1 Response Assessments**

Patients will be evaluated for response to treatment every 2 cycles  $\pm 5$  days up to 24 weeks (if 28 day cycle) or up to 18 weeks (if 21 day cycles), then every 12 (or 9, respectively) weeks  $\pm 5$  days, and, if clinically indicated, imaging of any other known or suspected sites of disease (e.g., brain).

The following assessments will be performed in addition to determination of elevated PSA levels (which will be taken on prior to dosing on Cycle 1 Day 1 as PSA baseline and on Day 1 of each subsequent cycle):

- CT/MRI scans of chest
- CT/MRI scan of the abdomen and pelvis
- Bone scan - technetium only

Lymph nodes and bone lesions should be evaluated using PCWG3 criteria ([Appendix B](#)) not RECIST v1.1. Patients with progressive disease or unacceptable toxicity should be discontinued from the study; patients with stable disease (SD) or response to therapy may continue treatment.

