### **7.5.3 Extended Follow-Up Period**

If treatment was discontinued for reasons other than disease progression, additional follow-up visits after the 30-day safety follow-up visit will be performed for tumor assessment by imaging as on treatment until PD or another withdrawal criterion is met:

- Start of a new anti-cancer therapy
- Lost to follow-up
- Death
- Patient withdrawal
- End of the whole study.

Additional PSA assessments after the 30-day safety follow-up visit will be performed as on treatment until PD or another withdrawal criterion is met.

These visits may also be performed by telephone interview or via written correspondence in case the patient is unable to visit the Investigator.

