### **Disease Progression will be defined as follows:**

#### **1) Bone Scan and Radiographic Progression**

Appearance of 2 or more new lesions on bone scan, and, for the first reassessment only, a confirmatory scan performed 6 or more weeks later that shows a minimum of 2 or more additional new lesions. The date of progression is the date of the first scan that shows the change.

Or

Soft tissue disease progression by modified RECIST v1.1.

Note that for some treatments, a lesion may increase in size before it decreases.

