#### **2) PSA Progression**

PSA progression is defined as  $\geq 25\%$  increase and  $\geq 2$  ng/mL increase above the nadir or baseline value for patients who had a PSA decrease on treatment, which is confirmed by a second value 3 or more weeks later.

For patients without a decrease on treatment, PSA progression is defined as  $\geq 25\%$  increase and an absolute increase of  $\geq 2$  ng/mL after 12 weeks.

PSA progressions must be confirmed at the next study visit 4 weeks later. PSA will be collected at screening and on Day 1 of each treatment cycle.

*CONFIDENTIAL*

Study Drug: AC176

Sponsor/Development Innovations Study Number: AC176-001/GU 207

Final Protocol: 10 July 2023 Version 4.0

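### PSA-only progression: Sections 3.3 and 5.2 do not carry over Appendix C's advice to continue treatment, and Section 7.5.3 sets a narrower condition for post-treatment imaging than footnote r of the treatment schedules

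*Protocol*

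**What the plan says.** **Stopping treatment.** Section 5.2 states: "Patients will continue on treatment until disease progression as defined in" Appendices B and C, or until side effects are not tolerated. Appendix C, under "Disease Progression will be defined as follows", has three numbered routes: bone scan or radiographic, PSA, and symptomatic. On the PSA route it adds that "PSA progressions must be confirmed at the next study visit 4 weeks later". Section 3.3 puts disease progression first among the reasons to discontinue, without distinguishing types. Its exception is that patients with clinical benefit in the Investigator's opinion "may be allowed to stay on study after consultation with the Medical Monitor".

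**Continuing treatment.** Appendix C, On-Study Disease Assessments, says: "Patients with PSA progression are allowed and encouraged to continue treatment until symptomatic or radiographic progression". Section 7.4 and the notes to the treatment schedules keep patients on drug while the Investigator judges that they benefit.

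**Imaging after treatment.** Section 7.5.3 begins: "If treatment was discontinued for reasons other than disease progression, additional follow-up visits", and these visits continue until PD or a listed withdrawal criterion such as new anti-cancer therapy or death. Footnote r of SOA 2, 3, 4 and 5 provides imaging "for patients who discontinue study treatment without having PD based on RECIST v1.1".

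**Endpoints.** Section 10.4.2 counts radiographic progression or death as the rPFS event. PFS and TTP also count PSA progression.

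**The concern.** There are two separate gaps, and both concern the patient whose only progression is by PSA.

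The first is whether he stops. A site that starts from Section 5.2 and follows its reference to the Appendix C definition finds PSA progression listed, and Section 3.3 then makes stopping the default, with a discretionary exception. A site that reads the preceding part of Appendix C finds continuing recommended. Sites may therefore treat the same patient differently.

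The second is whether he is still scanned if he does stop. PSA progression is not an rPFS event, so radiographic follow-up has to go on after it if rPFS is to be observed. If imaging ends at a PSA-only stop, rPFS is cut off in patients with a rising disease marker, and that censoring may be informative. The same holds for DoR where the ending event would be radiographic. A statistical analysis plan can set censoring rules, but it cannot recover scans that were never taken.

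**Working it through.** The protocol gives no figure on this point to reproduce. The check is a side-by-side reading, followed by a schedule illustration.

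**Step 1. Is PSA-only progression a reason to stop?**
- Section 5.2 with the Appendix C list: yes, once confirmed.
- Section 3.3: disease progression stops treatment by default. Staying needs clinical benefit and a Medical Monitor consultation.
- Appendix C, On-Study Disease Assessments: continuing is recommended, with neither condition stated.
- Section 7.4 and the schedule notes: continue while benefiting; PSA is not mentioned.

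The text specific to these patients favours continuing. The two sections that set the stopping rule are silent on it.

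**Step 2. Is a patient who stopped for PSA-only progression scanned afterwards?**
- Section 7.5.3: no, if the stop is recorded as disease progression.
- Footnote r in SOA 2 to 5: yes, because he has no RECIST v1.1 progression.

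Footnote r has its own gap: it names RECIST v1.1 only, while Table 7 and Appendix C also count PCWG3 bone progression as radiographic.

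**Step 3. What could be lost in one patient?** Take the 28-day schedules, with scans every 8 weeks to week 24 and then every 12 weeks: weeks 8, 16, 24, 36 and 48. Take a patient with no PSA decline. A rise at C4D1 (week 12) confirmed at C5D1 gives a stop at week 16; a rise at C5D1 confirmed at C6D1 gives a stop at week 20. In both cases the last scheduled scan is week 16. Assume no radiographic progression is seen. The start of new therapy is also assumed, since Section 7.5.3 and footnote r both end imaging then.

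| New therapy starts | Scans owed by footnote r but not by 7.5.3 | Follow-up beyond week 16 |
|---|---|---|
| before week 24 | none | 0 weeks |
| weeks 24 to 36 | week 24 | 24 − 16 = 8 weeks |
| weeks 36 to 48 | weeks 24 and 36 | 36 − 16 = 20 weeks |

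**Step 4. Allow for Section 7.5.1.** It requires imaging at discontinuation without PD unless done within the past 4 weeks; whether PD there includes PSA is not stated.
- Stop at week 16: the week-16 scan is recent enough even at an end-of-treatment visit 14 days later (18 − 16 = 2 weeks), so the table stands.
- Stop at week 20: the week-16 scan is at the limit (20 − 16 = 4 weeks), and a later visit exceeds it. If a scan is taken at week 20 to 22, the 8 weeks shrinks to between 24 − 22 = 2 and 24 − 20 = 4, and the 20 weeks to between 36 − 22 = 14 and 36 − 20 = 16.

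**Step 5. What is not touched?** DLTs are assessed in Cycle 1, before these events. For PFS and TTP the confirmed PSA progression is itself the event, so later scans do not change its date.

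**The case against.** The strongest reply is that the protocol can be read without conflict. Section 5.2 refers to Appendix C, and the only sentence there about managing PSA progressors tells them to continue; a specific instruction normally governs a general list. Section 3.3 does not name PSA and already allows patients to stay. Section 7.4 and the schedules point the same way. On imaging, Section 7.5.3 forbids no scan, and a site that works from its schedule follows footnote r and loses nothing. Loss requires a chain: PSA-only progression, a stop despite Appendix C, the stop recorded as disease progression, Section 7.5.3 followed over the schedule, and no new therapy before the next scan.

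Much of this stands, and it rules out several stronger inferences that a reader might draw:
- **That the protocol requires PSA-only progressors to stop.** On balance it favours continuing. The defect is that Sections 3.3 and 5.2 do not say so.
- **That Section 7.4.1 settles it.** It says "Patients with progressive disease or unacceptable toxicity should be discontinued from the study", but it follows the lymph-node and bone-lesion rule and contrasts progressive with stable disease or response, which is radiographic language.
- **That Section 10.4.2 independently requires these scans.** Its sentence says what is measured at follow-up visits before new therapy or death. It does not define who has such visits.
- **That footnote r undermines itself by citing Section 7.5.3.** The pointer follows its mention of withdrawal criteria, which that section lists. It does not import the section's entry condition.

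What survives is that Section 7.5.3 and footnote r set different conditions for the same follow-up, and that a site can apply Section 7.5.3 as written.

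**Conclusion.** The point holds as two wording defects. Sections 3.3 and 5.2 leave PSA-only progression to be read as a stopping event although Appendix C advises otherwise, and Section 7.5.3 defines eligibility for post-treatment imaging more narrowly than footnote r.

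The consequence is limited to secondary endpoints: rPFS, and DoR where progression is radiographic. The illustration of 0, 8 or 20 weeks concerns one hypothetical patient and rests on assumed dates for new therapy; a discontinuation scan under Section 7.5.1 can shorten it. A reader might infer that the rPFS estimate will be materially biased. The protocol does not support that: it gives no rate of PSA-only stops and no indication of how many sites would follow Section 7.5.3 over the schedule. The effect is possible, in the direction of early and potentially informative censoring, and of unknown size. Because the scans cannot be recovered later and the remedy is only wording, the correction is worth making at the next amendment.

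**What to change.** 1. **Section 7.5.3:** replace the entry condition with discontinuation without radiographic progression (RECIST v1.1 soft tissue or PCWG3 bone, Appendix B). For imaging, change the end point from PD to radiographic PD.
2. **Footnote r of SOA 2, 3, 4 and 5:** name PCWG3 bone progression beside RECIST v1.1.
3. **Sections 3.3 and 5.2:** state, by reference to Appendix C, that PSA progression alone does not require discontinuation. Whether a Medical Monitor consultation is still wanted for these patients is for the sponsor to decide. Section 3.3 can be read to require one and Appendix C does not waive it, so dropping this oversight in a first-in-human study would be a choice and not a clarification.

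The cost is wording in three sections and one footnote repeated in four schedules. Changing the Section 7.5.3 condition adds no scans beyond those footnote r already requires.

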### **Disease Progression will be defined as follows:**

#### **1) Bone Scan and Radiographic Progression**

Appearance of 2 or more new lesions on bone scan, and, for the first reassessment only, a confirmatory scan performed 6 or more weeks later that shows a minimum of 2 or more additional new lesions. The date of progression is the date of the first scan that shows the change.

Or

Soft tissue disease progression by modified RECIST v1.1.

Note that for some treatments, a lesion may increase in size before it decreases.

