### **7.5 Follow-Up Periods and Study Completion**

#### **7.5.1 End-of-Treatment Visit**

The EOT visit will be performed as soon as possible (preferably within 7 days but no later than 14 days) after permanent discontinuation of the study treatment for any reason, or when the Investigator decided with the patient to permanently discontinue the study treatment, or when the Investigator became aware that the study treatment had been discontinued.

*CONFIDENTIAL*

Study Drug: AC176

Sponsor/Development Innovations Study Number: AC176-001/GU 207

Final Protocol: 10 July 2023 Version 4.0

The assessments of the EOT visit will then be performed at the next planned visit. If the patient finishes treatment without having progressive disease (PD), tumor assessment/imaging must be performed at the time of treatment discontinuation unless it has been done within the past 4 weeks.

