## **9. RESPONSE EVALUATIONS AND MEASUREMENTS**

Response and progression will be evaluated in this study using RECIST Version 1.1 and PCWG3 criteria (see [Appendix B](#) and [Appendix C](#)). Lesions are either measurable or non-measurable according to the criteria. The term “evaluable” in reference to measurability will not be used, as it does not provide additional meaning or accuracy.

Lymph nodes and bone lesions should be evaluated using PCWG3 criteria (see [Appendix B](#)) not RECIST v 1.1.

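### Appendix C counts 2 or more new bone lesions on scans after the first reassessment as progression without confirmation, whereas Appendix B requires confirmation; a smaller mismatch affects PSA confirmation

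*Protocol*

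**What the plan says.** **Bone.** Appendix C, item 1, counts 2 or more new bone-scan lesions as progression and asks for confirmation "for the first reassessment only, a confirmatory scan performed 6 or more weeks later". Appendix B, under Bone scan progression, applies the 2+2 rule to the first post-treatment scan. For later scans it adds that "at least 2 new lesions relative to the first post-treatment scan should be confirmed on a subsequent scan", and on dating: "The date of progression will be the date of the scan that first documents the second lesion".

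**Which appendix governs.** Section 5.2 states "Patients will continue on treatment until disease progression as defined in" Appendix B and Appendix C. Section 9 states "Response and progression will be evaluated in this study using RECIST Version 1.1 and PCWG3 criteria" and again cites both. Section 7.4.1 says "Lymph nodes and bone lesions should be evaluated using PCWG3 criteria" and names Appendix B alone. The second paragraph of Section 9 does the same, and Table 7, which combines soft tissue and bone, sits in Appendix B. No order of precedence is given.

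**Endpoints.** rPFS is assessed by the study Investigator. PFS and TTP include radiographic progression, and duration of response ends at documented progression (Section 10.4.2).

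**PSA.** The TTP definition (synopsis, Table 3, Section 10.4.2) requires a confirming value 3 or more weeks later for patients whose PSA had decreased. For patients without a decrease it states no confirmation. Section 7.4.2 and Appendix C, item 2, add that every PSA progression is to be confirmed at the following visit, which they place 4 weeks later.

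**The concern.** Two rules in the current text give different answers to the same scan. A site that follows Appendix C records progression when 2 new lesions appear at week 16. A site that follows Appendix B waits for a further scan, and records no bone event if the lesions are not confirmed. Because the Investigator's reading is the endpoint, the choice of appendix enters rPFS directly and can also end a patient's treatment.

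An analysis rule written later may not fully repair this. Section 7.5.1 says "If the patient finishes treatment without having progressive disease (PD), tumor assessment/imaging must be performed", so the discontinuation scan is tied to the absence of progression. Section 7.5.3 continues imaging when treatment stopped for reasons other than progression. Once progression has been recorded under Appendix C, the scan that Appendix B needs may not be taken.

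**Working it through.** The protocol gives no event count, power or expected rate for rPFS, PFS or TTP, so there is no figure to reproduce. The check compares the rules and works out the visit spacing.

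**1. The bone rules side by side**

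| Scan with 2 or more new lesions | Appendix B | Appendix C | Agree? |
|---|---|---|---|
| First post-treatment scan | 2 additional lesions on the next scan | 2 additional lesions, 6 or more weeks later | Yes, apart from the 6-week minimum |
| Later scan, then confirmed | Event, dated to the scan that first documents the second new lesion | Event, dated to the first scan showing the change | Yes; normally the same date |
| Later scan, never confirmed | No bone event | Event | **No** |

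**2. Where the conflict starts.** On 28-day cycles (Table 2) scans fall at weeks 8, 16, 24, 36 and 48. Week 8 is the first reassessment, so the conflict starts at week 16. On 21-day cycles (Table 16) scans fall every 6 weeks at first, so it starts at week 12.

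**3. Wait for the next scheduled scan.** Each scan has a window of ±5 days, so the interval is the nominal gap ±10 days.
- 28-day cycles, week 16 to 24: 56 ± 10 = 46–66 days.
- 28-day cycles, week 24 to 36 and later: 84 ± 10 = 74–94 days.
- 21-day cycles, early scans: 42 ± 10 = 32–52 days.
- 21-day cycles, later scans: 63 ± 10 = 53–73 days. Table 16 makes this change at week 24; Section 7.4.1 makes it earlier: "up to 18 weeks (if 21 day cycles), then every 12 (or 9, respectively) weeks".

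Under Appendix B an unconfirmed finding usually gives no bone event before that next scan. Death, soft-tissue progression, unscheduled imaging or a discontinuation scan (due if the last imaging is more than 4 weeks old) can intervene.

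**4. Scale, under assumptions that are not in the protocol.** Take exponential progression with median m, and let a share q of event-free patients show unconfirmable lesions at each scan after the first. Then S_B(t) = 0.5^(t/m) and S_C(t) = S_B(t) × (1 − q)^k, where k is the number of scans after the first up to t. With m = 24 weeks, at week 24 (k = 2):
- S_B = 50.0%.
- q = 2%: 50.0% × 0.98² = 48.0%.
- q = 5%: 50.0% × 0.95² = 45.1%.
- q = 10%: 50.0% × 0.90² = 40.5%.

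Over m = 16, 24 and 36 weeks and these q, the gap is about 1 to 12 percentage points at week 24 and about 1 to 14 at week 48. The scan at which the curve reaches 50% is the same under both rules in every case, although these medians were set at scan weeks. The gap goes to zero as q does.

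**5. PSA.** Day 1 visits carry ±2 days, so consecutive visits are the cycle length ±4 days.
- 28-day cycles: 28 ± 4 = 24–32 days, nominally the stated 4 weeks and always at least 21 days.
- 21-day cycles: 21 ± 4 = 17–25 days. The maximum of 25 is below 28, so scheduled on-treatment Day 1 visits cannot meet 4 weeks. Follow-up visits (±5 days) are 21 ± 10 = 11–31 days apart and can.

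Example on 28-day cycles, patient without a PSA decrease: a qualifying rise at Cycle 5 Day 1 (112 ± 2 = 110–114 days) falls back at Cycle 6 Day 1. The TTP sentence read alone allows an event at Cycle 5 Day 1. Under Section 7.4.2 the earliest later PSA event is Cycle 7 Day 1, 56 ± 4 = 52–60 days afterwards.

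**The case against.** The best reply is that the protocol already assigns bone to Appendix B. That appendix is titled for RECIST in soft tissue and PCWG3 in bone, while Appendix C is titled for PSA. Sections 7.4.1 and 9 send bone lesions to Appendix B by name, Table 7 is there, and Section 10.4.2 attaches Appendix B to PCWG3-modified RECIST under ORR. The joint citations could mean Appendix B for imaging and Appendix C for PSA and symptoms. This stands as evidence of which rule to keep. It does not cancel the other rule: Appendix C presents its list as the definition of disease progression, and bone is its first item.

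A reader might infer that the affected data cannot be recovered. The documents do not support that. Footnote r of the schedule of assessments continues imaging for patients without RECIST progression, and bone is not evaluated by RECIST, so a patient with bone-only progression may still be imaged. The schedule footnotes also call for End of Study scans if none were taken in the previous 8 weeks (6 on 21-day cycles), and Section 3.3 lets patients with clinical benefit stay on. The risk of a missing scan is real but not general.

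A reader might also infer that the TTP text drops PSA confirmation altogether. It does not: it keeps confirmation for patients with a decrease, and it invokes the PCWG3 PSA criteria, which Appendix C sets out with the general confirmation sentence. The TTP wording can fairly be read as a shortened copy, which is why the PSA part is minor.

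**Conclusion.** The bone point holds. The appendices disagree on unconfirmed new lesions after the first reassessment, and both are cited for progression. Event status for rPFS, PFS, TTP and duration of response, and the decision to stop treatment, can differ from week 16 on 28-day cycles or week 12 on 21-day cycles. Confirmed findings are normally dated alike, so the difference is confined to findings that are never confirmed.

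The PSA point holds only for patients without a PSA decrease, together with the 4-week interval on the optional 21-day schedule.

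The share of patients affected cannot be derived from the protocol, and the percentage-point range above rests wholly on assumed rates. The spacing assumes scheduled visits without dose delay, and Appendix B's confirmation wording is read as a requirement. The endpoints are secondary and descriptive. It would be wrong to infer a threat to dose finding, since the MTD depends on Cycle 1 toxicity alone. The change should be made, but the study does not depend on it.

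**What to change.** **Bone.** Replace the bone rule in Appendix C, item 1, with a reference to the Appendix B rule and its dating, and have the rPFS, PFS and TTP definitions refer to that rule. Carrying Appendix C's 6-week minimum for the first-scan confirmation into Appendix B is optional. On 28-day cycles the next scan always meets it (46–66 days against 42). On 21-day cycles (32–52 days) it may not, and the minimum could then push confirmation past the next scan, so this should be a deliberate choice.

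**PSA.** In Section 7.4.2 and Appendix C, replace the 4-week sentence with one rule: a confirming PSA value at least 3 weeks later, in all patients. Refer to it from the TTP and PFS definitions. On 28-day cycles the next Day 1 always qualifies. On 21-day cycles, if the next Day 1 falls short of 21 days, use the following one (42 ± 4 = 38–46 days).

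**Cost.** Wording only, in Appendix C (items 1 and 2), Section 7.4.2, and the endpoint definitions in the synopsis, Table 3 and Section 10.4.2, plus one clause in Appendix B if the 6-week minimum is kept. No assessments are added.
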